A combination of physical therapist ([name]), summer research assistant/fellow, and employed certified athletic trainer ([name]) will be assigned to follow through on data collection for the entirety of the follow up period. The research assistant and athletic trainer will have access to patient name, and contact information. They will be authorized to telephone the patient to remind them to fill out their follow up PRTEE and NPRS. If the subject has not filled out their online survey after the 3 standard emails, we will attempt to contact the subject by phone. Each patient may be contacted 3 times, with each phone call one week apart at each follow up time point (3, 6, 12 months). If they have not filled out their survey at that point, we will cease attempts. The subject may ask us not to contact them by phone at any time, and we will not follow up by phone for the remainder of the study.

The final survey will include questions on whether the patient has sought and received other treatment, such as: prescribed medication, surgical intervention, injection therapy, and return to physical therapy.

Serious adverse events will be reported to the IRRB at any time during the active treatment phase of physical therapy, and will be entered into REDCap. This data will also be directly communicated to primary investigators-[name]; [name]; [name], DPT by email and phone. Mild adverse events, such as muscle pain and bruising at the site of BFR cuff will be considered routine and communicated only if it limits ability to treat patient at follow up visits, or leads to alteration in care.

Data Points collected will include:

1. PRTEE and NPRS will be collected at the physical therapy visit at entry, and sixth or last therapy visit. It will be collected electronically by email, with phone call reminders if necessary at 3 months, 6 months, and 12 months from the date of enrollment.
2. Grip Strength (maximum and maximum pain free), and 1 repetition maximum will be collected at entry into study, and 6th / or last visit.

Statistical Analysis

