BFR training has been shown to be safe and can also be applied to persons with various kinds of physical condition including cerebrovascular diseases, orthopedic diseases, obesity, cardiac diseases, neuromuscular diseases, diabetes, hypertension, and respiratory diseases. Nakajima performed a national survey of over 12,000 patients and found that the number of severe side effects is very low. The most frequent side effect is subcutaneous hemorrhage that is transient. Several papers showed that BFR training combined with low-intensity exercise does not cause severe muscle injury, and there is no elevation of creatine phosphokinase (CPK)²⁶ or rhabdomyolysis, as compared with heavy exercises.

Risks include primarily the risk of failure of physical therapy. As we know that therapy has variable responses with this condition, the possibility that the patient does not respond well to either control, or intervention treatment is real.

Medical risks appear very unlikely, with no significant side effects beyond muscle pain reported with BFR in the past.

KAATSU training, which is a Japanese version of blood flow occlusion training, has shown risks of major side effects to be less than 0.1% on a national survey of those using it. These risks included venous thrombo-embolism and rhabdomyolysis.

We believe significant side effects are very unlikely based on published data, and the idea that a trained therapist will be supervising the treatment of our patients.

We cannot envision any significant risk beyond muscle soreness, and possibly skin bruising for patients who have been enrolled in the intervention arm.

Serious Adverse events

Any significant adverse event-such as a venous thrombo-embolism, or significant medical event occurring within 48 hours of treatment will be recorded and reported.

If any significant similar medical event (such as a pulmonary embolism, angina episode, etc.) occurs in patients in any way which indicates a pattern of risk in the intervention group, the investigators will meet to discuss discontinuation of the trial.

Compensation for Injuries

No compensation for injury is planned. Subjects will be informed at the time of consent that any adverse event will be treated and covered as usual by the patient and their health insurance.

Benefits to Subjects

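### Mild BFR harms are likely to be under-counted: muscle pain and cuff bruising are exempted from routine communication, no data point covers them, and the safety-monitoring section conflicts with the exemption

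*Combined protocol and SAP*

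**What the plan says.** The Data Collection section sets two rules. Serious events go to the review board and into the REDCap database: "Serious adverse events will be reported to the IRRB at any time during the active treatment phase of physical therapy, and will be entered into" (the sentence ends by naming that database). They are also passed directly to the principal investigators. Mild events are handled differently. The examples given are painful muscles and bruises under the cuff, and the rule is that such an event "will be considered routine and communicated only if it limits ability to treat patient". A second trigger in the same sentence is a change in the patient's care.

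The Serious Adverse Events section covers thrombo-embolic events too, and says that any "significant medical event occurring within 48 hours of treatment will be recorded and reported". The numbered list of data points in Data Collection holds PRTEE, NPRS, grip strength and 1-repetition maximum. Neither that list, the Outcomes section nor the Statistical Analysis section contains an adverse-event item, a question put to patients at visits, or a comparison of harms by arm.

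The Risks and Side Effects section describes what is expected from BFR: "The most frequent side effect is subcutaneous hemorrhage that is transient". It foresees nothing of significance in the intervention arm apart from sore muscles and perhaps bruised skin.

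The Data/Safety Monitoring section is broader. Therapists, patients and blinded assessors are to contact the investigators about any adverse-event concern, and the safety line of the monthly checklist is not limited to serious events.

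**The concern.** The exempted events are the very harms that the plan names as expected. A trial of 44 patients has almost no chance of observing the rare serious events, so local tolerability is most of what it could learn about the safety of BFR in this new use.

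The exemption is also not neutral between arms. Only the BFR arm wears a cuff, so cuff bruising has no counterpart in the control arm. According to the Blinding section, the treating therapists know the allocation, and they are the people placed to judge whether an event limited or altered care. A later statement on tolerability, or a decision to extend BFR to other tendinopathies or to osteoarthritis as the Long Term Goals foresee, would rest on filtered reports. The discontinuation discussion in Data/Safety Monitoring starts from a suspicion of consistent adverse outcomes in the BFR arm, and that too depends on what reaches the investigators.

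**Working it through.** **1. How many events would the stated recording route capture?** The background text cites survey rates of 0.055% (venous thrombosis), 0.008% (pulmonary embolism) and 0.008% (rhabdomyolysis). Their sum is 0.055 + 0.008 + 0.008 = 0.071%, which agrees with the figure of under 0.1% in Risks and Side Effects. Assume these rates apply per patient to the 22 BFR patients:

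- At 0.071%: expected count 22 × 0.00071 = 0.016; chance of at least one, 1 − (1 − 0.00071)^22 = 1.6%.
- At 0.1%: expected count 22 × 0.001 = 0.022; chance of at least one, 1 − (1 − 0.001)^22 = 2.2%.

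For the serious events named in the survey, the category with a stated route will almost surely be empty. Nearly all observable BFR harm would be of the mild kind.

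**2. What might the communication filter do?** The documents give neither the rate p of mild events per BFR patient nor the share f of affected patients whose event limits or alters care. Both are assumed here, with patients independent. Patients affected = 22p. Patients communicated = 22pf. Chance that none is communicated = (1 − pf)^22.

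| p (assumed) | Affected of 22 | Communicated, f = 5% to 25% | Chance of none, f = 5% to 25% |
|---|---|---|---|
| 10% | 2.2 | 0.1 to 0.6 | 90% to 57% |
| 30% | 6.6 | 0.3 to 1.7 | 72% to 18% |
| 50% | 11 | 0.6 to 2.8 | 57% to 5% |

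The direction is fixed: the communicated count falls short of the true count whenever f is below 1. The amount is not fixed, and the range is wide.

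**3. What would a count of zero mean?** With 0 of 22, the one-sided 95% upper bound is 1 − 0.05^(1/22) = 12.7%. The exact two-sided 95% limit is 1 − 0.025^(1/22) = 15.4%. Both are valid only if every patient's events were ascertained.

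**4. The sections side by side.** Data Collection exempts mild events from communication unless one of two triggers is met. Data/Safety Monitoring asks for any concern to be reported and for adverse events in general to be on the monthly agenda. The second gives no form, definition or grading, and it does not withdraw the exemption. A therapist who sees a bruise that does not affect care is told by one section not to pass it on and by the other to report it if it raises concern.

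**The case against.** The strongest case on the other side has five parts.

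- **Communication is not recording.** A reader might infer that the plan forbids recording mild events, or that only serious events go into REDCap. The text does not say so. The exemption governs communication, and the word *only* is attached to communication and not to REDCap entry. Therapy encounters are also documented as usual in the health record. This stands as a limit on the claim. However, no route from those notes into the trial data is described. A REDCap appendix is listed, but its content is not in the available text, so whether a field exists there cannot be checked.
- **Data/Safety Monitoring exists.** A reader might infer that local signs could never reach the monthly review. That section does not support this; followed literally, it would shrink the under-count. What stands is a conflict between sections, and hence *likely* rather than *certain* under-counting.
- **Events that alter care are passed on.** True, and these matter most clinically. The remaining gap concerns events short of that.
- **The size is not known.** A reader might infer that reported tolerability would look near zero whatever happened. At p = 50% and f = 25%, the chance that nothing is communicated is only 5%. Nor would a bound of 12.7% be false in every case: a true rate of 10% lies below it.
- **Safety is not a stated aim.** Both specific aims concern function, pain and grip strength, and muscle soreness is expected in both exercise arms. Treating it as routine for urgent communication is defensible. That is a reason to leave the communication rule alone, but it does not justify leaving mild events without a data point.

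**Conclusion.** The point holds in this form: mild BFR harms are likely to be under-counted in the trial data. Three features of the text support it: an explicit exemption of the expected harms, a stated recording route for serious or significant events only, and no data point or analysis for mild ones. The filter would also act unevenly between arms, because one exempted event is specific to the cuff and the judgement falls to unblinded therapists. Data Collection and Data/Safety Monitoring conflict and must be reconciled.

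No size can be derived from the documents. The illustrative range depends wholly on the assumed p and f; for example, 0.3 to 1.7 communicated out of 6.6 affected at p = 30%. The 1.6% to 2.2% chance of any serious event assumes that the cited survey rates apply per patient. The primary PRTEE comparison is not affected. The change is worth making because it is cheap, and events missed at a visit may not be recoverable later.

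**What to change.** At each therapy visit in both arms, put one standard question to the patient and enter the answer in REDCap: has any adverse event (for example muscle pain, bruising or numbness) occurred since the last visit, and how severe was it? In the Statistical Analysis section, add a table of n (%) by arm with exact confidence intervals. Put the cumulative counts on the monthly meeting checklist.

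Reword Data Collection so that the present restriction applies to expedited communication only, and align it with Data/Safety Monitoring so that therapists have one instruction.

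The cost is a small amount of therapist time, at most 44 × 6 = 264 short entries. The Blinding section already has these therapists recording grip strength at each visit, so no extra visit, procedure or staff is needed. The answers will still come from unblinded patients and therapists, but a fixed question asked in both arms replaces a discretionary filter.

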 - a. We will also collect this data at final in person therapy visit, 3 months, and 6 months from baseline. These will be considered secondary outcomes.

Secondary Outcomes:

1. Change in Numeric pain rating scale (NPRS) from baseline visit to 12 months.
2. Change in maximum pain free grip strength from baseline to final therapy visit.
3. Change in maximum grip strength from baseline to final therapy visit
4. We will provide descriptive statistics as to whether subjects have sought other treatment after finishing our treatment protocol. This data will be collected as part of the 3, 6, 12 month contacts.
 - a. Other treatments sought will include: further doctor's visits, oral medications prescribed, injection therapy (and what type), surgical treatment.

The NPRS and PRTEE are validated, standardized outcome measures commonly used when assessing lateral epicondylitis. Assessing grip strength is standard practice, however, we wished to differentiate between maximum grip strength vs pain limiting grip strength.

Long Term Goals

The long term goals depend somewhat on the outcome of the trial. If the new BFR device shows promise and is seen to be superior to standard therapy, there is potential to evaluate its use in multiple types of chronic degenerative tendinopathy. There is also the potential to decrease the number of patient visits to therapy offices, increasing the value of therapy if it is effective. We also see the potential to apply to other degenerative conditions such as osteoarthritis to see if there is potential to improve therapy techniques and benefits for conditions such as these.

Research Design and Methods

Brief Design Description

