This will be a randomized, controlled, open label trial. A total of 44 subjects will be recruited. Each group will be divided equally with 22 subjects having been diagnosed with lateral elbow pain. Subjects will be recruited from CCAG physicians located within the CCAG health system, as well as at physical therapy locations at Health and Wellness Centers in Bath, Green, and Stow. A team of physical and occupational therapists have been recruited including therapists and athletic trainers who are present at each office. At each site, 1 therapist will undergo a 2 hour standardized training session on delivery of treatment and data collection. Patients evaluated and found to have the appropriate criteria by either physicians or physical therapists will be given a research information sheet (see appendix) offering the opportunity to participate in a research study at the above mentioned locations. The patients interested will be consented by phone, or in person once they present to physical therapy office.

Timeline of Study

The goal is a 6-week treatment period at 1 PT visit per week. In ideal situation the visits occur in consecutive weeks, but will be considered per protocol with 6 visits over a 12 week period. Follow up will occur for 12 months after the initial therapy visit. We anticipate the total open period of time to last between 2-3 years for completion of 1 year follow up, 2019-2022.

- A patient can elect to drop from the study at any time.
- A patient's treatment will be considered completed if they cannot attend 6 visits within the 12 week time frame.
- A patient can be discharged from care prior to 6 weeks if all clinical goals set at the initial therapy assessment are met. If this occurs the outcomes measures expected at the 6th visit will be recorded at this visit and considered equivalent to the 6th visit outcomes.

Recruitment/Enrollment

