Patients and treating therapists will be aware of the treatment rendered. Patients will self-enter their answers on the PRTEE and NPRS at the first, and 6th or final physical therapy visit. This data will either be self-entered to REDCap website, or onto paper copy which will be entered into REDCap by researcher blinded to their allocation. The treating physical therapists will be blinded to these results. Grip strength, and maximum pain free grip will be recorded at each therapy visit by treating physical therapist who is not blinded to the treatment allocation. We have made this decision understanding the risk of biasing a secondary outcome, but the burden of having multiple therapists at each site accommodate the institutional expectations for participating in research in order to have blinded assessment, has made this a necessity. Post treatment assessment with the NPRS and the PRTEE will be done via online REDCap survey. A researcher blinded to allocation will be responsible for contacting patients not responding to email contact to request completion of the online survey. A separate researcher, blinded to group allocation will analyze the final results that will be stored in REDCap.

Device

We will be using the Delfi personalized tourniquet system for BFR in this study (Delfi Medical Innovations Inc., [name]). The Delfi system allows a specific limb occlusion pressure to be applied to a patient's limb in order to reduce their arterial flow by a proscribed amount. In our project, we will use 50% occlusion as the standard ²².

Physical therapy staff participating in the study will be trained on the use of BFR technology. At least one therapist will attend formal training provided by the device developer prior to beginning enrollment in the study. After receiving training, all other participating therapists will be trained by the therapist/s who have received formal training.

Statement from the manufacturer (received via email):

The Delfi PTS Personalized Tourniquet System for BFR device when used according to the device's Intended Use and Indications for Use statements in the Operator and Maintenance Manual is cleared for market under Delfi Medical Innovations Inc.'s FDA Device Listing for Pneumatic Tourniquets E127474 as a Class I device exempt from premarket notification procedures. Delfi Medical Innovations Inc. is a registered establishment with the FDA under registration number 9681444.

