The study population proposed is readily accessible at Cleveland Clinic Akron General as a review specifically of Akron General Orthopedic practitioners over a 10 month period covering 2017-2018 showed over 200 office visits with the diagnosis code for lateral epicondylitis. Cleveland Clinic Akron General as a facility has the adequate resources available to support the study, including electronic medical records and REDCap. In addition, qualified and experienced medical staff members will conduct the study, including a sports medicine physician, two doctors of physical therapy with residency training in sports medicine, research coordinator/biostatistician, and a master's level athletic trainer. The authors will also apply for summer research interns as part of the annual Cleveland Clinic Akron General program. Co-investigators will be trained on the protocol and only IRRB approved staff will be conducting research related procedures.

Outcomes assessment

Numeric Pain Rating Scale (NPRS), Patient Rated Tennis Elbow Evaluation (PRTEE)

For the NPRS, subjects will be asked to rate their pain 0-10, with 0 being no pain and 10 being worst pain imaginable. Subjects will be asked to rate their least pain in the last 3 days and worst pain the last 3 days.

For the PRTEE, it will be issued in paper or electronic format to the patient prior to physical examination.

In both cases, the scales will be collected on the first/baseline visit, as well as at the final therapy visit (if known). They will then be collected electronically by email (with phone call reminders if necessary) at 3, 6, and 12 months.

Grip Strength Testing

The subject will be given a calibrated hand dynamometer and will be instructed to keep arm adducted and elbow bent to 90 degrees while in a sitting position. The subject will be asked to squeeze until onset of pain that is 2 points above resting pain on NPRS. There will be two attempts, with 60 seconds in between, and the average will be recorded. Then, using the same positioning, the subject will perform 2 max effort squeezes within their pain tolerance. The average of the two measure will be recorded as done previously.

Therapy Protocols

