Once randomized, Twenty-two subjects will be placed into a control group, in which standard loading of the wrist and finger extensors using 70% of 1 Rep max (RM), determined using a 1 RM calculator, will be given as well strengthening pronators, supinators and grip strength. The experimental group of 22 will receive blood flow restricted wrist extensor strengthening at 50% limb occlusion using 20% of their 1 RM. To assess 20% of 1 RM of the extensors, a weight will be given to the patient to see how many repetitions can be performed. The weight and number of reps will be entered into a 1 RM calculator so that 20% of the 1 RM can be determined. Strengthening using BFR will occur once per week in clinic, in addition to standard strengthening of supinator, pronators and grip strength. They will also perform the same standardized home exercise program as the control group. All participants will receive the same instruments at baseline and 6th visit. Treatment performed at the three participating clinics will undergo standardized training in the use of BFR strengthening as well as specific study protocol training prior to the onset of the study.

The subjects placed into the control group will receive standard loading of the wrist and finger extensors using 70% of 1 Rep max (RM). The subject will be given the appropriate weight in clinic to be able to do 3 sets of 15. The subject will also strengthen pronators, supinators using a weighted stick to a 7 out of 10 on a rate of perceived exertion (RPE) scale. Grip strength will be addressed using therapeutic putty, resistance determined by the therapist's assessment, having the patient perform 3 sets of 2 min of squeezing the putty. The therapist will have discretion on if cervical spine, thoracic spine or shoulder treatment is warranted, based on standard practice. This treatment will occur for 6 visits in the clinic.

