The subjects in the experimental group will use weighted dumbbells to find 20% of their 1 RM for their wrist extensors, as described above. Once that is found, a portable tourniquet system will be applied to the upper arm to achieve partial vascular occlusion, set to 50% of their predetermined total limb occlusion pressure (LOP). To determine the total limb occlusion pressure (LOP), a tourniquet will be inflated around the subject's upper arm to begin vascular occlusion. The model used will be a Delfi Personalized Tourniquet System, allowing safe control and regulation of blood pressure throughout exercise. This will continue until a Doppler ultrasound will no longer be able to detect a pulse. The amount of pressure found to create pulse absence will be that subjects personal LOP and be used to determine the amount of occlusion needed to achieve 50% limb occlusion.

The subject will perform 4 sets in total for the wrist extensor exercise. One set of 30 reps followed by 3 sets of 15. Subjects will have 30 seconds of rest between sets while the tourniquet remains inflated. Subjects will have a 1 min rest break in between exercises. The subjects will also perform resisted supination, pronation using 3 sets of 15 and grip strengthening using therapeutic putty for 3 sets of 2 min while using the tourniquet set at 50% of their LOP. Resistance will be adjusted to ensure patients are achieving 7 out of 10 effort on RPE scale. Additional treatment to the cervical spine, thoracic spine and shoulder will be at the discretion of the therapist. This treatment will occur for 6 visits in the clinic.

If the patient is unable to complete the expected number of repetitions at the expected resistance a standardized adjustment to the protocol will take place:

- If they complete 60-74 total repetitions: continue with training but extend rest period between sets 3 and 4 to 45 seconds, until 75 total reps are complete.
- If they complete 45-59 total repetitions: continue with training but extend rest period between all sets to 45-60 seconds.
- If they complete less than 44 total repetitions: reduce load by 10% until 75 reps achieved.

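### Grip strength has two differing visit schedules, and under one of them patients who stop treatment unexpectedly can have no post-baseline grip value (secondary outcomes only)

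*Combined protocol and SAP*

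**What the plan says.** The Outcomes section defines two grip endpoints: "Change in maximum pain free grip strength from baseline to final therapy visit" and "Change in maximum grip strength from baseline to final therapy visit". Three places then bear on when grip is measured.

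- **Blinding:** "Grip strength, and maximum pain free grip will be recorded at each therapy visit by treating physical therapist".
- **Data Collection, list of data points:** "Grip Strength (maximum and maximum pain free), and 1 repetition maximum will be collected at entry into study, and 6th / or last visit".
- **Therapy Protocols:** "All participants will receive the same instruments at baseline and 6th visit". This sentence does not name grip, but it fits the two-occasion schedule.

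On patients who do not complete six visits, Timeline of Study has two relevant rules. If a patient is discharged early because the clinical goals are met, the sixth-visit measures are taken at that visit and count as such. For patients who fall short for other reasons, it says "A patient's treatment will be considered completed if they cannot attend 6 visits within the 12 week time frame" and asks for no closing assessment. Patients may also withdraw whenever they wish.

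The PRTEE and NPRS are collected again at 3, 6 and 12 months. Grip is not. Grip Strength Testing describes posture, number of attempts and averaging, but does not say whether the test comes before or after that visit's exercise.

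**The concern.** Aim 2 rests on grip, and both grip endpoints need a value at the final therapy visit. When a patient simply stops coming, nobody knows at the time that the visit just attended was the last. A site working from the Data Collection list would have had no reason to test grip that day, and no later contact could supply the value.

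The grip comparison would then leave out patients who stopped unexpectedly. That selection happens after randomisation. It could differ between arms because the in-clinic regimens differ, although the documents give no figures on this.

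The choice of schedule also changes the dataset. Statistical Analysis uses visit number as a factor for primary and secondary outcomes. Grip has two time points under one schedule and up to six under the other.

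**Working it through.** **Step 1. The schedules side by side.**

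| Patient | Data Collection schedule (entry; sixth or last visit) | Blinding schedule (every visit) |
|---|---|---|
| Completes six visits | Baseline and final value | Baseline and final value |
| Planned early discharge | Final value taken at discharge | Final value taken at discharge |
| Stops without notice after at least one post-baseline visit | Can have no post-baseline value | Has a value from the last attended visit |
| Under six visits in 12 weeks, last visit not recognised at the time | Can have no post-baseline value | Has a value from the last attended visit |
| No visit after baseline | None | None |

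The schedules give different data only in the third and fourth rows. The one-repetition maximum shares the Data Collection line but is absent from the Blinding sentence, so there is no conflict to reconcile for it. This point is limited to the two grip measures.

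**Step 2. The plan's own figure.** The documents give no sample size, standard deviation or target difference for grip. The only calculation is for the PRTEE (Power Analysis: SD 10, difference 10, two-sided 0.05, power 80%, 17 per group). The normal approximation is n = 2 × (1.96 + 0.84)² × (10/10)² = 15.7, so 16. The two-sample t test gives 16.71, so 17, with power 0.807 at 17. The stated figure reproduces, but it does not bear on grip.

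**Step 3. Scale under the Data Collection schedule.** The proportion stopping unexpectedly during treatment is not given, so 10% to 30% is an assumption. Number affected = proportion × 44. Remaining per arm = 22 × (1 − proportion), rounded down. The last column is the difference detectable with 80% power by a two-sided 0.05 two-sample t test, in SDs of the change in grip.

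| Assumed proportion | Affected of 44 | Remaining per arm | Detectable difference |
|---|---|---|---|
| 0% | 0 | 22 | 0.86 SD |
| 10% | 4.4, about 4 | 19.8, so 19 | 0.93 SD |
| 20% | 8.8, about 9 | 17.6, so 17 | 0.99 SD |
| 30% | 13.2, about 13 | 15.4, so 15 | 1.06 SD |

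The 30% row is near a ceiling. Power Analysis gives 30% as the dropout allowance for the PRTEE, whose primary endpoint is at 12 months, whereas the treatment period is six weeks and at most 12.

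**Step 4. Where the values are kept.** Blinding says the analyst works from results stored in REDCap. Potential Limitations says therapists record grip results in the patient charts. Even if grip is tested at every visit, nothing states that the interim values reach the analysis dataset.

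**The case against.** The strongest reply is that the two schedules can be read together. The Data Collection list says what the data points will include and does not exclude others. Grip could be charted at every visit, with the list naming the two values that form the endpoint. A patient who stops after visit 3 would then have a charted visit-3 value that serves as the last one. This reading is possible, and on it no value is lost at the clinic. But the documents do not state it, do not say that charted interim values go into REDCap, and do not say that the last attended value counts as final.

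Four stronger inferences are tempting, and the documents do not support them.

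- A reader might infer that Outcomes assessment concedes the loss of grip data, because it schedules a measurement "as well as at the final therapy visit (if known". That sentence is about the NPRS and PRTEE. It concerns the same final visit, but the grip paragraph has no such qualifier.
- A reader might take 30% as the expected loss of grip data. It is a 12-month PRTEE allowance, not a rate of stopping treatment.
- A reader might infer that acute fatigue will distort one arm's grip results, because the experimental arm does "grip strengthening using therapeutic putty for 3 sets of 2 min while using the tourniquet set at 50% of their LOP". The control arm does the same putty work without the cuff, and no passage says grip is tested after exercise. Any difference between arms, and its direction, cannot be derived from the documents.
- A reader might infer a threat to the main result. The primary outcome is the PRTEE at 12 months, which does not depend on grip.

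**Conclusion.** The point holds in limited form. The plan gives two grip schedules and does not say which governs. Under the entry-and-last-visit schedule, unplanned stoppers can have no post-baseline grip value, and nothing later replaces it. Under the every-visit schedule, only patients with no visit after baseline lack one.

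The number at risk is unknown. On the assumption of 10% to 30% unexpected stopping, it is about 4 to 13 of 44, and the detectable difference rises from 0.86 SD to between 0.93 and 1.06 SD. Selection that differs by arm is possible but not shown. The consequence is confined to the secondary grip outcomes under Aim 2. The change is still worth making before enrolment, because a grip value that was never taken cannot be recovered.

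**What to change.** 1. Amend the Data Collection list, and the instrument sentence in Therapy Protocols, to agree with Blinding: both grip measures at every therapy visit, entered in REDCap.
2. State that grip is tested before that visit's exercise in both arms. This is a precaution, since the order is unstated.
3. Define the final-visit grip value as the one from the last attended post-baseline visit, and keep change from baseline to that value as the endpoint.
4. If all visits are analysed, make that supportive and use a mixed model for repeated measures, which keeps patients with incomplete visits under a missing-at-random assumption. Repeated measures ANOVA in its standard form deletes patients with any missing visit, and so would drop the partial attenders this change is meant to keep.

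The cost is protocol and form wording plus slightly more data entry. Blinding already commits therapists to the measurements, so no visits or staff are added. One limitation remains: the last attended value comes after different amounts of treatment in different patients, so the number of visits attended should be reported by arm alongside it.
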